9.2.5 SUBGROUP ANALYSIS

In addition to the analyses described above secondary endpoints will be analysed split by the subgroups described in section 6.6, as appropriate.

If additional subgroup analyses are needed, the details will be included as an amendment to this SAP prior to database release.

9.2.6 SUMMARY OF ANALYSES

Outcome	Analysis Set	Supports Protocol Objective Number	Subgroups	Statistical Method	Covariates/Strata	Missing Data
Number of Treatment Escalations	FAS			Cox- Proportional hazards with recurrent events (Section 9.1.1)	Covariates: DAS28-4(ESR) ≤ 3.2 , Δ DAS28- 4(ESR) > 1.8 , PtGA, PhyGA,	Imputation

				Pain, Satisfaction Confounders: Age, Gender, Duration of disease, Indicator of tofacitinib dose, Poor prognostic factors (PF) Indicator, Indicator of dose of MTX or combination partner, Indicator of dose of Glucocorticoids, Whether patient on 2 nd or 3 rd line treatment, Indicator of tolerability issues, Indicator of efficacy issues, comorbidities: Ischemic cardiovascular disease, Malignancies, Infections, Gastro disease, Osteoporosis, Depression (Note: will be assessed as individual covariates or as a composite, with 1 if a patient has any comorbidity or 0 otherwise, as appropriate).	
Number of Treatment Escalations	PPAS		Cox- Proportional hazards with recurrent events (Section 9.1.1)	Covariates: DAS28-4(ESR) ≤ 3.2, ΔDAS28- 4(ESR) > 1.8, PtGA, PhyGA, Pain, Satisfaction Confounders: Age, Gender, Duration of disease, Indicator of tofacitinib dose, Poor prognostic	No Imputation

					factors (PF) Indicator, Indicator of dose of MTX or combination partner, Indicator of dose of Glucocorticoids, Whether patient on 2 nd or 3 rd line treatment, Indicator of tolerability issues, Indicator of efficacy issues, comorbidities: Ischemic cardiovascular disease, Malignancies, Infections, Gastro disease, Osteoporosis, Depression (Note: will be assessed as individual covariates or as a composite, with 1 if a patient has any comorbidity or 0 otherwise, as appropriate).	
Number of Treatment Escalations (Sensitivity Analysis)	FAS			Cox- Proportional hazards with recurrent events (Section 9.1.1)	Covariates: DAS28-4(ESR), ΔDAS28 4(ESR), PtGA, PhyGA, Pain, Satisfaction, Comorbidities (1 if patient has any comorbidity, 0 otherwise). Confounders: Age, Gender, Duration of disease, Indicator of tofacitinib dose, Poor prognostic factors (PF) Indicator, Indicator of dose of MTX or combination partner,	No Imputation

					Indicator of dose of Glucocorticoids, Whether patient on 2 nd or 3 rd line treatment, Indicator of tolerability issues, Indicator of efficacy issues, If the overall comorbidity covariate is significant the individual comorbidity covariates (Ischemic cardiovascular disease, Malignancies, Infections, Gastro disease, Osteoporosis, Depression) may be included as confounders instead as appropriate.	
Number of Treatment Escalations (Sensitivity Analysis)	PPAS			Cox- Proportional hazards with recurrent events (Section 9.1.1)	Covariates: DAS28-4(ESR), Δ DAS28-4(ESR), PtGA, PhyGA, Pain, Satisfaction, Comorbidities (1 if patient has any comorbidity, 0 otherwise). Confounders: Age, Gender, Duration of disease, Indicator of tofacitinib dose, Poor prognostic factors (PF) Indicator, Indicator of dose of MTX or combination partner, Indicator of dose of Glucocorticoids, Whether patient on 2 nd or 3 rd line treatment,	No Imputation

					Indicator of tolerability issues, Indicator of efficacy issues. If the overall comorbidity covariate is significant the individual comorbidity covariates (Ischemic cardiovascular disease, Malignancies, Infections, Gastro disease, Osteoporosis, Depression) may be included as confounders instead as appropriate.	
Number of Treatment Escalations (where treatment switch is assigned to prior visit – further sensitivity)	FAS			Cox- Proportional hazards with recurrent events (Section 9.1.1)	Covariates: DAS28-4(ESR) ≤ 3.2 , Δ DAS28-4(ESR) > 1.8 , PtGA, PhyGA, Pain, Satisfaction Confounders: Age, Gender, Duration of disease, Indicator of tofacitinib dose, Poor prognostic factors (PF) Indicator, Indicator of dose of MTX or combination partner, Indicator of dose of Glucocorticoids, Whether patient on 2 nd or 3 rd line treatment, Indicator of tolerability issues, Indicator of efficacy issues, comorbidities: Ischemic cardiovascular disease, Malignancies,	Imputation

					Infections, Gastro disease, Osteoporosis, Depression (Note: will be assessed as individual covariates or as a composite, with 1 id a patient has any comorbidity or 0 otherwise, as appropriate).	
Number of Treatment Escalations (where treatment switch is assigned to prior visit – further sensitivity)	PPAS			Cox- Proportional hazards with recurrent events (Section 9.1.1)	Covariates: DAS28-4(ESR) ≤ 3.2, ΔDAS28- 4(ESR) > 1.8, PtGA, PhyGA, Pain, Satisfaction Confounders: Age, Gender, Duration of disease, Indicator of tofacitinib dose, Poor prognostic factors (PF) Indicator, Indicator of dose of MTX or combination partner, Indicator of dose of Glucocorticoids, Whether patient on 2 nd or 3 rd line treatment, Indicator of tolerability issues, Indicator of efficacy issues, comorbidities: Ischemic cardiovascular disease, Malignancies, Infections, Gastro disease, Osteoporosis, Depression (Note: will be assessed as individual covariates or as a composite, with 1 id a patient has any	No Imputation

					comorbidity or 0 otherwise, as appropriate).	
Time to First Treatment Escalation	FAS			Kaplan-Meier Plots and Table (Section 9.1.2)		No imputation
Rate of LDA	FAS, including only data collected with patient remained on tofacitinib		Therapy Sequence, RA Medication History, Switch Status, Number of Treatment Switches (Section 6.6)	Summary Tables (Section 9.1.4)		No imputation
Rate of Remission	FAS, including only data collected with patient remained on tofacitinib		Therapy Sequence, RA Medication History, Switch Status, Number of Treatment Switches (Section 6.6)	Summary Tables (Section 9.1.4)		No imputation
Change from baseline DAS28-4	FAS, including only data collected with patient remained on tofacitinib		Therapy Sequence, RA Medication History, Switch Status, Number of Treatment Switches (Section 6.6)	Summary Tables (Section 9.1.3)		No imputation
Change from baseline in Morning Stiffness	FAS, including only data collected with patient remained on tofacitinib		Therapy Sequence, RA Medication History, Switch Status, Number of Treatment Switches (Section 6.6)	Summary Tables (Section 9.1.3)		No imputation
Change from baseline in FFbH	FAS, including only data collected with		Therapy Sequence, RA	Summary Tables (Section 9.1.3)		No imputation

	patient remained on tofacitinib		Medication History, Switch Status, Number of Treatment Switches (Section 6.6)			
Rate of functional remission in FFbH	FAS, including only data collected with patient remained on tofacitinib		Therapy Sequence, RA Medication History, Switch Status, Number of Treatment Switches (Section 6.6)	Summary Tables (Section 9.1.4)		No imputation
Change from baseline in EQ-5D score	FAS, including only data collected with patient remained on tofacitinib		Therapy Sequence, RA Medication History, Switch Status, Number of Treatment Switches (Section 6.6)	Summary Tables (Section 9.1.3)		No imputation
Change from baseline in FACIT score.	FAS, including only data collected with patient remained on tofacitinib		Therapy Sequence, RA Medication History, Switch Status, Number of Treatment Switches (Section 6.6)	Summary Tables (Section 9.1.3)		No imputation
Drug Survival	FAS			Kaplan-Meier Plots and Table (Section 9.1.2)		No imputation
Patient's Satisfaction with Drug Treatment	FAS,		Therapy Sequence, RA Medication History, Switch Status, Number of Treatment Switches	Summary Tables (Section 9.1.5)		No imputation

			(Section 6.6)			
--	--	--	------------------	--	--	--

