2 AMENDMENTS FROM PREVIOUS VERSION(S)

The Protocol A3921302_ObservationalPlan_Finalv1.1_23Aug2017.docx states that:

In order to collect comparable study data, visits 2 to 9 occurring +/- 14 days of the scheduled visit date will be used for data analysis.

As the visits will be scheduled according to clinical practice there are likely to be many visits outside of the windows defined in the protocol. To ensure the primary analysis incorporates all visits at which a patient might experience a treatment escalation all visits will be included. A further per-protocol analysis will be conducted using the analysis windows set out in Section 12.1.1.

Populations used during interim analyses were updated.

Additional details regarding the definition of the primary endpoint were added, because the definition provided in the protocol was not specific enough. Escalations were classified into 3 different types: Step-up, step-down or termination. The analysis of the primary endpoint will be conducted overall and per escalation type. A table with all possible treatment type changes has been added together with the corresponding type of escalation.

The assignment of escalations occurring in-between scheduled visits has been mostly aligned with that for the secondary endpoints for consistency across analyses and for greater precision of the assignment. In addition, imputation rules for missing values of covariates to be included in the analyses of the primary endpoint, have been added.

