8 HANDLING OF MISSING VALUES

8.1 TIME TO EVENT (PRIMARY ANALYSIS, TIME TO FIRST TREATMENT ESCALATION AND DRUG SURVIVAL)

Time to event should be determined for the events without any date imputation.

If a patient experiences the event of interest the status will be 1, and the time will be the time at which the event occurred (or visit at which it was recorded).

If a patient doesn't experience the event of interest the status will be 0, and the time will be the last time that the patient was known to be in the study (last visit). If this is not the end of the study then the time will be censored at this time point.

The primary endpoint is a time-to-event endpoint, although it takes into account the possibility of multiple events occurring for each patient. For each patient the data for analysis should consist of the times at which they experienced the event of interest and the values of the covariates at each time point. Any missing data within the covariates to be included in the models for primary analysis will be replaced by the nearest available value to the event. If more than one value qualifies, the later value will be used .

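### The FAS sensitivity model with continuous DAS28 also switches off imputation and alters the comorbidity terms, so a changed hazard ratio could not be traced to the DAS28 cut-points

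*SAP*

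**What the plan says.** SAP 8.1 holds the operative rule. Its stated scope is "Any missing data within the covariates to be included in the models for primary analysis". Under this rule a gap "will be replaced by the nearest available value to the event", with the later one taken when two are equally near. The list of changes in SAP section 2 describes this as "imputation rules for missing values of covariates to be included in the analyses of the primary endpoint, have been added".

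SAP 9.2.6 then sets the missing-data rule model by model. The FAS row "Number of Treatment Escalations", which uses DAS28-4 (ESR) at or below 3.2 and a change above 1.8 as yes/no terms, is imputed. So is the FAS model that assigns each switch to the prior visit. The FAS row "Number of Treatment Escalations (Sensitivity Analysis", which uses DAS28 and its change as continuous terms, reads "No Imputation". All three PPAS rows read the same.

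The FAS continuous row also adds a factor of interest: "Satisfaction, Comorbidities (1 if patient has any comorbidity, 0 otherwise". Its confounder list then adds a condition: "If the overall comorbidity covariate is significant the individual comorbidity covariates" may be used instead. The primary row has no such condition. It enters the six comorbidities singly or as a composite, whichever is judged appropriate.

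SAP 9.2.2 introduces the sensitivity analyses as a change of covariates and says nothing about a different missing-data rule.

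**The concern.** The natural use of the FAS continuous model is to show whether the results depend on cutting DAS28 at 3.2 and its change at 1.8. For that, it should differ from the primary model in the coding alone.

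As written, it also drops imputation. SAP 9.1.1 fits PROC PHREG to start/stop rows with covariate values in each row. With no imputation, a row that lacks any model covariate leaves the fit, and its risk time and any event in it go too. The two models would then be fitted to different rows. If their hazard ratios differ, the coding, the lost rows and the comorbidity terms are all possible causes. If they agree, the reassurance about the cut-points is weaker than it looks.

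There is a related gap. No FAS model applies the primary specification to complete rows, so nothing tests the nearest-value rule itself. That rule fills in a single value and, through its tie-break, can use one recorded after the event.

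**Working it through.** The plan states no figure for this point, so there is none to reproduce. The check compares the rows of the table and then illustrates the possible loss of rows.

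**Step 1. The six primary-endpoint models in SAP 9.2.6**

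| Set | Model | DAS28 terms | Missing covariates | Comorbidity terms |
|---|---|---|---|---|
| FAS | Primary | yes/no | imputed | six single terms or a composite |
| FAS | Continuous DAS28 | continuous | not imputed | composite as factor of interest; single terms conditional |
| FAS | Prior visit | yes/no | imputed | as primary |
| PPAS | Primary | yes/no | not imputed | as FAS primary |
| PPAS | Continuous DAS28 | continuous | not imputed | as FAS continuous |
| PPAS | Prior visit | yes/no | not imputed | as FAS primary |

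**Step 2. What each comparison changes**

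- FAS primary against FAS continuous: coding, missing-data rule and comorbidity terms (three changes).
- PPAS primary against PPAS continuous: coding and comorbidity terms. Imputation is held fixed, but the visits are restricted to the windows.
- FAS continuous against PPAS continuous: the visit set only.
- FAS primary with and without imputation: not planned.

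**Step 3. Items a complete row needs**

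DAS28-4 (ESR) needs TJC28, SJC28, ESR and PtGA (SAP 7.1.2.4.1). The model adds PhyGA, pain and satisfaction (SAP 7.3.1 and 7.3.2). PtGA is already counted, so the total is 4 + 3 = 7 visit items. The yes/no and continuous codings need the same seven, so coding alone would not change which rows are complete. Dose-change indicators are not counted.

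The four baseline components of the DAS28 change are left out of this contrast. SAP 12.1.1 does not impute a missing baseline and excludes the patient from change-from-baseline analyses. On that reading the loss falls on both models.

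**Step 4. Share of rows kept without imputation**

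Protocol 7.8 and 7.12 expect missing items but give no rate. Let m be an assumed missing rate.

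- Seven independent items: share kept s = (1 − m)^7.
- Four independent blocks (joint counts; ESR; the patient-reported items; PhyGA), each missing as a whole at rate m: s = (1 − m)^4. The grouping is an assumption.

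For scale, take a factor with a nominal 80% power on all rows and assume events are lost in the same proportion as rows. Then power = Φ(√s × (1.960 + 0.842) − 1.960).

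| m | s, 7 items | power | s, 4 blocks | power |
|---|---|---|---|---|
| 3% | 0.97^7 = 0.808 | 71% | 0.97^4 = 0.885 | 75% |
| 5% | 0.95^7 = 0.698 | 65% | 0.95^4 = 0.815 | 72% |
| 10% | 0.90^7 = 0.478 | 49% | 0.90^4 = 0.656 | 62% |

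**Step 5. Does losing rows move the estimate?**

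Not necessarily. A small simulation used assumed values: 60 runs, 1500 patients, 8 intervals each, and one DAS28-type covariate with a true log hazard ratio of 0.4 per point. The mean coefficient was 0.375 (SE 0.032) with nothing missing and 0.371 (SE 0.035) with 20% of rows missing at random. It was 0.366 (SE 0.032) when 5% of event rows and 25% of other rows were missing. Missingness that depends on disease activity itself was not simulated. The result supports no claim of bias. The problem shown here is one of attribution.

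**The case against.** The strongest reply is that the plan already separates coding from imputation, because the two PPAS models share one missing-data rule. That stands in part. A reader might infer that the FAS continuous model is the plan's only check on the cut-points, and the table does not support that. The PPAS pair is nonetheless an imperfect substitute, since its comorbidity terms change too and it uses only in-window visits.

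A reader might also infer that the PPAS rows are wrong. The documents do not show this. SAP 6.5 limits the PPAS to data from scheduled visits inside the windows, while the nearest-value rule has no window limit and could bring in values from outside them. All three PPAS rows say the same thing, which looks deliberate.

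It can further be said that the table agrees with 8.1, whose wording reaches only the models for the primary analysis. That is a fair reading, and section 2 is only a list of changes, so I do not rest a contradiction on it. But the prior-visit model is a sensitivity analysis as well, and it is imputed. The scope of the rule therefore remains unclear.

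Finally, the loss of rows may be small. That is true: no missing rate is given, and items collected together tend to go missing together. Counting the four baseline items as well would give a larger loss, but 12.1.1 appears to apply that loss to both models.

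**Conclusion.** The point holds, within limits. Among the three FAS models, only the continuous-DAS28 model drops imputation, and no reason is given. Followed as written, the FAS check on the cut-points changes three things at once, and a difference from the primary model could not be attributed to any one of them.

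The size of the row loss is unknown. The range shown, from 89% of rows kept (3% missing, four blocks) to 48% (10% missing, seven independent items), rests entirely on assumed rates, on the assumed pattern of missingness and on complete-row fitting, which the SAP does not spell out.

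A reader might infer that the primary result is compromised. It is not: the primary FAS estimate is untouched, and only the interpretation of its sensitivity analysis suffers. The change should be made because it is cheap and lets that analysis answer its question, but it is not critical to the study.

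**What to change.** 1. In SAP 9.2.6, set the FAS continuous-DAS28 row to the missing-data rule of the FAS primary model (8.1).
2. Use the primary model's comorbidity terms in that comparison, so that only the DAS28 coding differs. Without this step, changing the table cell alone would still leave two differences.
3. Add one run of the unchanged FAS primary model on complete rows only, so that the effect of the nearest-value rule is seen separately.
4. State in 8.1 which models the rule covers, including the prior-visit FAS model.
5. Leave the PPAS rows without imputation.

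The cost is one table cell, a change to one covariate list, one sentence in 8.1 and one extra model run. No new data are needed. SAP 9.1.1 analyses escalations overall and by three types, so the extra run would be four fits if repeated for each type; the overall fit would be enough for this purpose.

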10 LIST OF TABLES AND TABLE SHELLS

To be presented in a separate document.

12 APPENDICES

12.1 APPENDIX 1: DATA DERIVATION DETAILS

12.1.1 A1.1 DEFINITION AND USE OF VISIT WINDOWS IN REPORTING

Visit windows will be used for efficacy variables, and for any safety displays that display by month. The visit windows for the analysis defined in the table differ from that outlined in the protocol. The analysis visit windows will be M1, M3±14 days, all subsequent visits MX ± 28 days.

Table 11.1: Visit windows

Visit Label	Target Day	Definition [Day window]
Enrolment	1	1
Month 3	91	77 to 105
Month 6	182	154 to 210
Month 9	273	245 to 301
Month 12	365	337 to 393
Month15	456	428 to 484
Month18	547	519 to 575
Month 21	638	610 to 666
Month 24	730	702 to 758

For the lab values, if the calculated study day for the labelled baseline visit is not study Day 1, but falls within 40 days before the start of the study dosing, then that data should be used for the baseline instead of leaving baseline missing.

For the other values, if the calculated study day for the labelled baseline visit is not study Day 1, but falls before the start of the study dosing, then that data should be used for the baseline instead of leaving baseline missing.

If baseline is missing there will be no imputation and although the subject's data will be included in summary data it will not be included in any change from baseline analyses.

If two or more visits fall into the same window, keep the one closest to the Target Day. If two visits are equal distance from the Target Day in absolute value, the later visit should be used.

For the primary endpoint analysis, escalations occurring in-between two planned visits will be assigned to visits using the visit windows described above. If two or more escalations

fall into the same window, all escalations will be counted. Escalations, which are assigned to the baseline visit, will be counted under the Month 3 Visit, unless the escalation occurred before first tofacitinib treatment. Escalations, which fall outside the visit windows, will be assigned to the visit nearest to the Target Day. If two visits are equal distance from the escalation date in absolute value, the later visit should be used.

(Safety analysis may follow Pfizer standard)

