7.5.2. Schedule of Activities

The schedule of activities table provides an overview of the visits that may be documented. Refer to the STUDY PROCEDURES and ASSESSMENTS sections of the protocol for detailed information on each documentation and assessment.

According to his clinical practice the HCP may schedule visits (unplanned visits) in addition to those listed on the schedule of activities, in order to conduct evaluations or assessments required to protect the well-being of the patient. As this is a non-interventional study none of these visits are mandatory and every visit should be scheduled according to clinical practice.

Table 7. Schedule of Activities

Study Week	Baseline (Enrolment)	Month 3	Month 6	Month 9	Month 12	Month 15	Month 18	Month 21	Month 24
Visit Number	1	2	3	4	5	6	7	8	9
Informed Consent	x								
Initial diagnosis of RA	x								
Prognostic factors	x								
Relevant comorbidities	x								
Demographic data	x								
Insurance type	x								
Smoking history and current smoking status	x								
Physical Examination (weight, height)	x								
Inclusion/Exclusion criteria	x								
Varicella vaccination status	x								
Prior drug treatment of RA	x								
RA-treatment with Tofacitinib and/or other DMARDs	x	x	x	x	x	x	x	x	x
Concomitant treatment of RA with Glucocorticoids	x	x	x	x	x	x	x	x	x

Tofacitinib citrate

A3921302 OBSERVATIONAL PLAN NON-INTERVENTIONAL STUDY

Final, 23 August 2017

Inflammatory Markers	x	x	x	x	x	x	x	x	x
Documentation of AE	x	x	x	x	x	x	x	x	x
Number of swollen and tender joints	x	x	x	x	x	x	x	x	x
Duration of Morning stiffness	x	x	x	x	x	x	x	x	x
Patient's Global Assessment of Arthritis	x	x	x	x	x	x	x	x	x
Physician's Global Assessment of Arthritis	x	x	x	x	x	x	x	x	x
Patient's Assessment of Arthritis Pain	x	x	x	x	x	x	x	x	x
Functional Ability Questionnaire Hannover (FFbH)	x	x	x	x	x	x	x	x	x
EuroQoL EQ-5D-3L	x	x	x	x	x	x	x	x	x
FACIT – Fatigue Scale	x	x	x	x	x	x	x	x	x
Patient's satisfaction with drug treatment	x	x	x	x	x	x	x	x	x

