3.1 STUDY DESIGN

This is a 60-month, prospective, non-interventional, multi-centre study to evaluate the impact of the following factors on the number of treatment escalations of tofacitinib patients in 24 months.

Eligible patients will be followed up from the date of first tofacitinib prescription for 24 months. Patients who are switched from the initial tofacitinib therapy to other therapies will also be followed up to 24 months. Patient documentation is expected quarterly as per standard clinical practice.

This study observes drug prescription and follow-up visits in daily medical care. Therapeutic strategies and frequency of patient follow-up are decided by the treating physician.

Figure 1. Study Design

The planned recruitment period is 36 months. With planned observation duration of 24 months per patient, the entire study would thus last for 60 months. The study started in October 2017 and, due to an extension of the recruitment period of 9 months, the study will end in July 2023. Overall, about 1500 patients in about 200 centres in Germany are to be included in this non-interventional study.

The schedule of activities table provides an overview of the visits that may be documented. Refer to the STUDY PROCEDURES and ASSESSMENTS sections of the protocol for detailed information on each documentation and assessment.

According to his clinical practice the HCP may schedule visits (unplanned visits) in addition to those listed on the schedule of activities, in order to conduct evaluations or assessments required to protect the well-being of the patient. As this is a non-interventional study none of these visits are mandatory and every visit should be scheduled according to clinical practice.

Table 1. Schedule of Activities

Study Week	Baseline (Enrolment)	Month 3	Month 6	Month 9	Month 12	Month 15	Month 18	Month 21	Month 24
Visit Number	1	2	3	4	5	6	7	8	9
Info1med Consent	x								
Initial dia21osis of RA	x								
Proimostic factors	x								
Relevant comorbidities	x								
Demographic data	x								
Insurance type	x								
Smoking history and cwTent smoking status	x								
Phvsical Examination (weight, height)	x								
Inclusion/Exclusion criteria	x								
Varicella vaccination status	x								
Prior drug treatment of RA	x								
RA-treatment with tofacitinib and/or other DMARDs	x	x	x	x	x	x	x	x	x
Concomitant treatment of RA with Glucocorticoids	x	x	x	x	x	x	x	x	x
InflammatoIY Markers	x	x	x	x	x	x	x	x	x
Documentation of AE	x	x	x	x	x	x	x	x	x

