6.2 FULL ANALYSIS SET

The Full Analysis Set (FAS) will include all patients who receive at least one dose of tofacitinib and have at least one post-baseline visit. The primary analysis will use the FAS. The FAS will include all data collected during the study, both scheduled and unscheduled visits.

The protocol states that patients will be enrolled if they fulfil all selection criteria for the study and are started on treatment with tofacitinib for moderate to severely active rheumatoid arthritis.

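### Gaps between the SAP's visit windows leave off-window efficacy measurements without a place in the by-month tables, most of all around Month 3

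*SAP*

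**What the plan says.** - **Scope.** SAP 12.1.1 opens with "Visit windows will be used for efficacy variables, and for any safety displays that display by month".
- **Widths.** The same section states "The analysis visit windows will be M1, M3±14 days, all subsequent visits MX ± 28 days". Its table gives days 77–105 for Month 3, 154–210 for Month 6, 245–301 for Month 9, and so on to 702–758 for Month 24.
- **Several visits in one window.** "If two or more visits fall into the same window, keep the one closest to the Target Day".
- **Outside all windows.** A rule exists for escalations only: "Escalations, which fall outside the visit windows, will be assigned to the visit nearest to the Target Day". SAP 12.1.1 also rescues baseline values recorded before dosing, but says nothing about a post-baseline measurement that falls between windows.
- **Visit timing.** Protocol 7.5.2 says "As this is a non-interventional study none of these visits are mandatory", and SAP 3.1 repeats this.
- **Reason for leaving the protocol's windows.** SAP 2 explains that "there are likely to be many visits outside of the windows defined in the protocol". The protocol's windows (Protocol 7.5) are ±14 days at every visit from 2 to 9.
- **By-month tables.** SAP 7.1.2.2, 7.1.2.3, 9.1.3 and 9.1.4 summarise endpoints at each time point. For the binary endpoints the denominator is patients with a non-missing value at that month. SAP 8.2 and 8.3 do not impute unless stated otherwise.
- **Primary analysis.** SAP 6.2 says "The FAS will include all data collected during the study, both scheduled and unscheduled visits", and SAP 9.2.2 uses that set for the main model.

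**The concern.** The study observes routine care, so visits will not fall neatly on target days. If a measurement between windows belongs to no month, and missing values are neither imputed nor counted in the denominator, data already collected disappear from the tables of low disease activity, remission, change in DAS28, morning stiffness, FFbH, EQ-5D and FACIT-Fatigue.

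Month 3 stands out. The SAP left the protocol's ±14 days because it expected many visits to miss them. It doubled the half-width from Month 6 on, yet kept ±14 days at Month 3 without giving a reason. The largest gap between windows comes straight after, inside the 3–6 month span that the study objective names for the DAS28 difference.

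At stake are precision and possibly bias in the descriptive curves. Protocol 7.12 itself warns that an as-observed analysis carries a risk of bias that grows with the amount of missing outcome data. Because the treating physician decides visit frequency (Protocol 7.1), the loss need not be random.

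**Working it through.** **1. Reproduce the SAP's table.** Target days are 91, 182, 273, 365, 456, 547, 638 and 730. Target ±14 for Month 3 gives 77–105. Target ±28 for the rest gives 154–210, 245–301, 337–393, 428–484, 519–575, 610–666 and 702–758. All eight windows match the table.

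**2. Count days in no window.**

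| Gap | Days |
|---|---|
| 106–153 | 48 |
| 211–244 | 34 |
| 302–336 | 35 |
| 394–427 | 34 |
| 485–518 | 34 |
| 576–609 | 34 |
| 667–701 | 35 |
| Total | 254 |

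Check: days covered = 29 + 7 × 57 = 428; span = 758 − 77 + 1 = 682; 682 − 428 = 254; 254/682 = 37.2%.

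The share depends on the range chosen. Adding days 2–76 (75 days) gives 329/758 = 43.4% of days 1–758.

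Between the Month 3 and Month 6 target days, both included, there are 182 − 91 + 1 = 92 days, of which 48 (52%) are unassigned.

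**3. Compare with the protocol's windows.** ±14 days at all eight visits covers 8 × 29 = 232 days. That leaves 682 − 232 = 450 uncovered, or 66.0%. The SAP's windows are a real improvement, but they still have gaps.

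**4. From days to visits (assumed scatter).** The documents give no distribution of visit dates. Assume they are normal and centred on target with standard deviation SD. The share falling outside a visit's own window of half-width h is 2 × [1 − Φ((h + 0.5)/SD)].

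| SD (days, assumed) | Month 3, h = 14 | Later visits, h = 28 |
|---|---|---|
| 14 | 30% | 4% |
| 21 | 49% | 17% |
| 28 | 60% | 31% |

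With tighter scatter the loss shrinks quickly: at SD 7 it is about 4% at Month 3 and close to nil later.

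**5. Effect of contiguous windows.** Cutting at midpoints between target days gives Month 3 = 46–136, Month 6 = 137–227 and so on, with Month 24 still ending at day 758. No day from 46 to 758 is then unassigned. The present table leaves (76 − 46 + 1) + 254 = 285 of those 713 days (40.0%) unassigned.

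**The case against.** The strongest reply is that the SAP never says off-window measurements are dropped. The set defined by windows is the PPAS (SAP 6.5). The SFAS (SAP 6.3) is defined by being on tofacitinib, with no window condition, and the summary table in SAP 9.2.6 adds none. Visits carry numbers and labels, so the by-month tables could be built on visit label, with the windows reserved for the per-protocol repeat that SAP 2 describes.

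Part of this stands: the loss is inferred from a missing rule, not from an instruction to discard. But the label reading sits badly with the first sentence of SAP 12.1.1, which applies the windows to efficacy variables without limiting them to the PPAS. SAP 2 also says that the assignment of between-visit escalations was mostly aligned with the approach for the secondary endpoints, which implies that those endpoints are windowed too. If labels are intended, the SAP needs to say so.

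Three further objections are sound and limit the point:

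- A reader might take the SAP to predict many visits outside its own windows. Its remark concerns the protocol's ±14 days, so it bears only on Month 3.
- A reader might suppose that early visits are flares and late visits are stable patients, and so infer a direction of bias. Neither document says this, and no direction or size can be derived.
- Wider windows have a cost. A Month 3 window of days 46–136 puts assessments up to 45 days from target under one label. Three interim analyses have already been run with the methods planned for the final one (SAP 4.1), so a change without a bridge would break comparability.

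**Conclusion.** The point holds for the by-month efficacy tables. Followed as written, SAP 12.1.1 leaves measurements on 254 of 682 days (37%, days 77–758) without a month, while escalations on the same days are given one. Month 3 is the weakest place: it has the narrowest window, the longest gap between windows follows it, and it keeps a width the SAP expects many visits to miss.

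It would be wrong to read 37% as the share of visits lost. Visits should cluster near target days, and the documents do not give their scatter. The figures of about 30–60% at Month 3 and 4–31% later rest wholly on an assumed normal scatter with SD 14–28 days.

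Nor does the point reach the main result. The primary FAS model uses all visits, and time to first escalation and drug survival are calculated from dates. What is affected is descriptive, without formal comparison between groups (SAP 9.1.6). This is a worthwhile, inexpensive improvement, not a threat to the primary conclusion.

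**What to change.** In SAP 12.1.1, for the by-month efficacy tables:

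- Assign each post-baseline measurement to the nearest target day, using contiguous windows cut at midpoints (Month 3: days 46–136; Month 6: days 137–227; and so on, with Month 24 ending at day 758). Send a day equidistant from two targets to the later one, as is already done for escalations.
- Keep the existing rule that the visit closest to target is used when two share a window.
- State how measurements on days 2–45 and after day 758 are treated.
- Keep the present windows for the PPAS, and repeat the by-month tables with them as a sensitivity version. This also preserves comparability with the interim analyses.
- Report, per month, the number of visits outside the present windows, so that the size of the effect is known rather than assumed.

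The cost is a second window table, programming and labelling of two window sets, and month labels that are less exact, most of all at Month 3. No new data are needed.
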